#### **12.2.3. Visit 2 (Day 2)**

Visit 2 will occur approximately 24 hours after administration of the intradermal injection of peptides. Subjects will have the option of an in person visit or a remote visit (i.e., telephone). Subjects will be asked if they have experienced any AEs or unusual skin reactions following administration of the IP.

If subjects opt for an in-person visit, photography of the injection sites (volar forearms) will be used for safety documentation of local site and any unexpected findings.

#### **12.2.4. Visit 3 (Day 3)**

The subject will return to the study site and the intradermal skin test will be read approximately 48 hours after administration of the intradermal injection of peptides. The basis of reading is the presence or absence of induration, which may be determined by inspection (from a side view against the light as well as by direct light) and by palpation.

The area of induration will be measured at injection sites on the volar forearms ([Section 12.1.10](#)). To ensure standardization, calipers will be used to ensure accurate measurement of induration. A member of the study team will visually inspect injection site under good light and measure the induration (thickening of the skin), not erythema (reddening of the skin). Measurements will be made across two diameters. The mean of the longest and midpoint orthogonal diameters of the indurated area should be reported as the DTH response.

The exact measurement of the induration in millimeters (mm) should be recorded in the subjects CRF.

Subjects will be asked if they have experienced any AEs or unusual skin reactions following administration of the investigational product. An AE occurring since the last visit will be documented in the subjects CRF.

Photography of the injection sites (volar forearms) will be used for safety documentation of local site and any unexpected findings.

#### **12.2.5. Visit 4 (Day 4)**

Visit 4 will occur in person approximately 72 hours after administration of the intradermal injection of peptides to conduct a brief medical review (general health inquiry) and to document AEs that occurred since the last study site visit.

The area of induration will be measured at injection sites on the volar aspect of both forearms.

Photography of the injection sites (volar forearms) will be used for safety documentation of local site and any unexpected findings.

**12.2.6. Visit 5 (Day 5)**

Visit 5 will occur in person approximately 96 hours after administration of the intradermal injection of peptides to conduct a brief medical review (general health inquiry) and to document AEs that occurred since the last study site visit.

The area of induration will be measured at injection sites on the volar aspect of each forearm.

Photography of the injection sites (volar forearms) will be used for safety documentation of local site and any unexpected findings.

**12.2.7. Visit 6 (Day 30)**

Visit 6 will occur by telephone approximately 30 days (720 hours) after administration of the intradermal injection of peptides to conduct a brief medical review (general health inquiry) and to document AEs that occurred since the last study site visit.

**12.2.8. Visit 7 (Day 180)**

Visit 7 will occur by telephone approximately 180 days after administration of the intradermal injection of peptides to conduct a brief medical review (general health inquiry) and to document AEs that occurred since the last study site visit.

## **13. STATISTICAL CONSIDERATIONS AND ANALYSES**

Before database lock, a detailed statistical analysis plan (SAP) will be developed and finalized, which will include full description of the statistical analyses and the exact definition of variables to be analysed.

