### **13.7. Interim Analysis**

The skin test DTH result assessments are obtained at Visits 3, 4 and 5 (48, 72 and 96 hours post administration of skin test). An interim analysis will be conducted after all subjects have completed Visit 5 (or early terminated prior to Visit 5), and a database lock of the efficacy and safety data up to Visit 5 will occur. The purpose of the interim analysis will be to assess the presence of DTH reactions in response to intradermal injection of synthesized TNX-2100 SARS-CoV-2 peptide antigens, and to assess safety up to 96 hours post-administration. A full database lock will occur after all subjects have completed Visit 7 (or early terminated prior to Visit 7).

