The planned analyses identified in this SAP may be included in clinical study reports (CSRs), regulatory submissions, or future manuscripts. Also, post-hoc exploratory analyses not necessarily identified in this SAP may be performed to further examine study data. Any post-hoc or unplanned, exploratory analysis performed will be clearly identified as such in the final CSR.

The final clinical database cannot be locked until the final SAP has been approved and signed.

2. Study Objectives and Endpoints

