2.3. Modified Evaluation

Because the outcome of area of induration for the DTH reactions was not as anticipated, the DTH reactions will not be statistically analyzed. Any primary, secondary, or exploratory efficacy endpoint will be omitted from the analysis and only safety will be assessed.

3. Overall Study Design and Plan

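### No rule requires the SAP to be signed before the Visit 5 lock, at which all skin-test readings are complete and DTH presence is analysed

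*Protocol*

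**What the plan says.** Protocol section 13 sets the timing of the SAP: "Before database lock, a detailed statistical analysis plan (SAP) will be developed and finalized". It does not say which lock is meant.

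Protocol section 13.7, like the synopsis, describes two locks. At the first, "a database lock of the efficacy and safety data up to Visit 5 will occur", once every subject has completed Visit 5 or left early. An analysis is run on those data, and its aim is stated: "The purpose of the interim analysis will be to assess the presence of DTH reactions in response to intradermal injection", together with safety to 96 hours. The second lock follows the Day 180 telephone call: "A full database lock will occur after all subjects have completed Visit 7 (or early terminated prior to Visit 7".

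SAP section 1 attaches signature to one lock only: "The final clinical database cannot be locked until the final SAP has been approved and signed". The SAP has no interim-analysis section, and its section 11 lists no other planned analysis.

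SAP sections 2.3 and 10 then drop all efficacy endpoints. The reason opens: "Because the outcome of area of induration for the DTH reactions was not as anticipated". Under SAP section 8.5 the DTH responses are listed by subject and visit, not summarised.

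**The concern.** A SAP guards against results-driven choices only if it is fixed before the results it governs are seen. The skin-test readings end at Visit 5, so the lock that matters for DTH is the first one. Neither sign-off sentence names it, and the SAP's sentence points to the other. The study is open-label, so blinding offers no second line of defence.

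What is at stake is the set of efficacy rules that the protocol leaves to the SAP. These decide which mixture, strength and reading time look best, and Protocol section 5.3 says the best-performing mixture and dilution go forward to a larger confirmatory study. A rule picked after seeing the readings would still carry the standing of a pre-specified one. The same gap lets a decision not to analyse be taken on the results.

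**Working it through.** The documents give no power, alpha or target estimate on this point, so there is no figure to reproduce. The check is of sequence first, then of what is still open.

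**Sequence**

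1. Skin-test readings are taken at Visits 3, 4 and 5 only (Protocol sections 12.2.4 to 12.2.6 and 13.7). Visits 6 and 7 are telephone visits and add no scheduled induration measurement.
2. Investigational sites per subject: 3 mixtures × 2 strengths = 6. Readings per subject: 6 sites × 3 visits = 18. All planned readings are complete at the Visit 5 lock.
3. The SAP's sign-off condition attaches to the final lock, after Visit 7. Nominal gap for the last subject: Day 180 − Day 5 = 175 days. This is visit spacing; actual lock dates are not given.
4. Protocol section 13 is compatible with either lock. SAP section 1 is compatible with signature at any time up to the final lock. No other passage requires signature before the Visit 5 lock.

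**What the protocol already fixes**

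- The 5 mm cut-off (sections 7.2.2.1 and 12.1.10).
- The response as the mean of two diameters (section 12.1.10).
- The ITT and mITT definitions (section 13.1), with mITT as the efficacy set (section 13.6).
- Counts and percentages at or above 5 mm, by cohort and overall (section 13.6).

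**What it leaves to the SAP**

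- How several sites and reading times combine into one positive result.
- How the best mixture, strength and reading time are chosen (objectives in section 6.2).
- The methods for sensitivity/specificity and for the correlations.
- The criterion for the T-cell immunodeficiency exclusion in section 13.6.

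**How much a late choice could matter (illustration only)**

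Candidates: 3 mixtures × 2 strengths × 3 reading times = 18. Let J = sensitivity + specificity − 1. Suppose all 18 have the same true accuracy and the one with the highest observed J is picked afterwards, with 30 subjects in each of two groups. The mean apparent J over 40,000 simulated trials, with correlation ρ between candidates on a latent normal scale, is:

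| Assumed sensitivity / specificity | True J | Best of 18, ρ = 0.8 | ρ = 0.5 | ρ = 0 |
|---|---|---|---|---|
| 0.50 / 0.90 | 0.400 | 0.524 | 0.557 | 0.590 |
| 0.70 / 0.90 | 0.600 | 0.716 | 0.746 | 0.773 |
| 0.843 / 0.95 | 0.793 | 0.884 | 0.905 | 0.921 |

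A single candidate fixed in advance averaged its true J to within 0.001. The accuracies and ρ are assumptions. The 0.843 matches the 43 of 51 positive reactions in the study of previously infected subjects cited in Protocol section 5.3 (43/51 = 0.843).

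**What the SAP text shows**

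Sections 2.3 and 10 give the induration outcome as the reason for omitting efficacy, so that text was written with the outcome known. Neither section says when the decision was taken relative to the Visit 5 lock.

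**The case against.** The strongest reply is that the protocol sentence may already be sound. Section 13.7 calls the Visit 5 event a database lock and the later one a full lock, so an unqualified reference can naturally mean the first. That reading is fair, and it makes the protocol ambiguous rather than clearly defective. It does not close the gap: on that reading the SAP's condition is laxer than the protocol's, and the two still need reconciling.

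A reader might infer that every analysis rule was open until the final lock. The documents do not support that, because the protocol fixes the cut-off, measurement, analysis sets and cohort frequencies.

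A reader might also infer that the SAP was signed after the Visit 5 analysis. That cannot be shown. No SAP date or lock date is visible in the text reviewed, an earlier plan may have existed, and in an open-label study the readings can be known before any lock. For the same reason, signature before the Visit 5 lock could still follow many of the readings. It would precede the locked analysis, but it is not complete protection.

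Nor is the interim analysis necessarily the whole efficacy analysis: its stated purpose is DTH presence and early safety, not the correlation or T-cell endpoints.

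Finally, the study is a descriptive proof of concept without a sample-size calculation. SAP section 1 already promises to label post hoc analyses in the study report, section 10 already gives the reason for the change, and the current SAP produces no efficacy estimate that could be inflated. This limits the consequence. It does not supply the missing sign-off rule or the timing of the change.

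**Conclusion.** The point holds in a limited form. Nothing in the two documents ensures that the efficacy rules left to the SAP are fixed before the DTH data are locked and analysed, and the SAP's own condition permits signature up to a nominal 175 days after the last subject's final reading. At that point 18 of 18 planned investigational readings per subject are complete. The exposure is confined to the four open items listed in the check.

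If the best candidate were chosen after the fact, the illustration puts the optimism in J at roughly 0.09 to 0.19 (0.884 − 0.793 = 0.091; 0.590 − 0.400 = 0.190), under the assumed accuracies and correlations and equal true performance. This measures the risk in the rule; it is not an estimate of bias in this trial's results.

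The current SAP text was written knowing the DTH outcome. Whether it came before or after the Visit 5 lock cannot be settled from the documents. The plan should be changed, but this is not a fatal flaw in a descriptive study.

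**What to change.** In Protocol section 13, state that the SAP will be finalised and signed before the Visit 5 lock and the interim analysis described in section 13.7.

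If that lock has not yet occurred, align SAP section 1 by making the Visit 5 lock conditional on the signed SAP.

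If it has occurred, do not rewrite the sign-off rule retroactively, since the new sentence might be untrue. Instead:

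- In SAP section 10, give the date of the change relative to the Visit 5 lock, and say that the decision on DTH analysis was made after the outcome was known.
- Still report the summary specified in Protocol section 13.6: counts and percentages with induration of 5 mm or more, by cohort and overall, in the mITT set. Showing it for each site and reading time avoids the need for a combination rule.
- Label any other efficacy rule post hoc, including any criterion for the T-cell immunodeficiency exclusion set after the data were seen.

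The cost is a few sentences and one descriptive table from data already collected, plus earlier sign-off where the lock is still ahead. No extra subjects or measurements are needed.

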### **13.1. Populations for Analysis**

The following analysis populations will be used during the study:

- Safety Population: includes any subjects in Cohort 1, 2, or 3 who receive at least 1 intradermal injection of the IPs.
- Intent-to-Treat (ITT) Population: includes any subjects in Cohort 1, 2, or 3 who provide written informed consent, satisfy all inclusion/exclusion criteria, and have a negative test result from PCR detection of SARS-CoV-2 viral RNA.
- Modified Intent-to-Treat (mITT) Population: includes subjects from ITT who complete stages 1 and 2 of administration and have induration responses for at least one post skin test administration visit at hour 48, 72, or 96.

### **13.2. General Considerations**

Tabulations will be produced for appropriate demographic and assay parameters. For categorical variables, summary tabulations of the number and percentage within each category of the parameter will be presented. For continuous variables, the mean, median, standard deviation, minimum and maximum values will be presented.

All descriptive statistical analyses will be performed using SAS statistical software (Version 9.4 or higher), unless otherwise noted. Medical History will be coded using Medical Dictionary for Regulatory Activities (MedDRA; dictionary Version 24.0).

### **13.3. Demographics**

Demographic characteristics (age, sex, ethnicity and race) and anthropometric characteristics (height, weight and BMI) will be listed by subject and summarized by cohorts using descriptive statistics for all subjects in the safety population.

- Age (years) at screening as continuous summary
- Sex
- Ethnicity
- Race

- Weight
- Height
- BMI

### **13.4. Subject Disposition**

The disposition of subjects who were enrolled (i.e., signed the ICF) in the study as well as reasons and the time period of discontinuation from the study and from treatment will be summarised for each treatment group (and overall).

### **13.5. Safety Analyses**

The safety of intradermally administered TNX-2100 SARS-CoV-2 peptides will be measured as detailed in [Section 7.2.1](#). All safety analyses will be conducted using the Safety Population.

#### **13.5.1. Adverse Events**

All AEs will be listed. The number and percent of subjects experiencing an event will be tabulated for each System Organ Class and Preferred Term. The AEs will also be tabulated according to severity and causality.

For this study, AESIs are anaphylactic reactions and enhanced disease from repeated exposure to SARS-CoV-2 (in subjects who have recovered from SARS-CoV-2 infection or in subjects recently vaccinated against SARS-CoV-2).

Serious AEs (SAE) will be listed separately.

#### **13.5.2. Clinical Laboratory Tests**

Individual data listings of laboratory results will be presented for each subject. Flags will be attached to values outside of the laboratory's reference limits along with the Investigator's assessment. Clinically significant laboratory test abnormalities that were considered AEs by the Investigator will be presented in the AE listings.

Clinical laboratory tests (observed values) will be summarized descriptively in tabular format. Shift tables will be presented for select laboratory parameters.

#### **13.5.3. Vital Signs**

Individual data listings of vital signs (observed and change from baseline) will be presented for each subject. Individual clinically significant vital signs findings that were considered AEs by the Investigator will be presented in the AE listings.

Observed values as well as change from baseline data will be summarized descriptively in tabular format.

#### **13.5.4. Physical Examination**

Abnormal physical examination findings will be listed.

### **13.6. Efficacy Analyses**

The efficacy analyses include primary, secondary, and exploratory endpoints as outlined in [Section 7.2.2](#). Efficacy analyses will be conducted using the mITT population.

The frequency and percentage of subjects with a maximal area of induration of  $\geq 5$  mm will be summarized within each cohort and by overall subjects.

Cytokine and cell surface T-cell phenotype markers will be summarized descriptively within each cohort and by overall subjects.

Enzyme linked immune assay parameters will be summarized descriptively by study visit within each cohort and by overall subjects.

Results obtained from subjects deemed to be T-cell-specific immunodeficient will be collected, documented and reported, but will not be included in the analysis of the efficacy of the assay to detect a DTH response to SARS-CoV-2 peptides.

### **13.7. Interim Analysis**

The skin test DTH result assessments are obtained at Visits 3, 4 and 5 (48, 72 and 96 hours post administration of skin test). An interim analysis will be conducted after all subjects have completed Visit 5 (or early terminated prior to Visit 5), and a database lock of the efficacy and safety data up to Visit 5 will occur. The purpose of the interim analysis will be to assess the presence of DTH reactions in response to intradermal injection of synthesized TNX-2100 SARS-CoV-2 peptide antigens, and to assess safety up to 96 hours post-administration. A full database lock will occur after all subjects have completed Visit 7 (or early terminated prior to Visit 7).

## **14. DEFINITIONS, RECORDING, AND REPORTING OF ADVERSE EVENTS**

### **14.1 Definition of Adverse Events**

Any untoward medical occurrence in a patient or clinical investigation subject administered a pharmaceutical product and which does not necessarily have a causal relationship with this treatment. An AE can therefore be any unfavorable and unintended sign (including an abnormal laboratory finding), symptom, or disease temporally associated with the use of a medicinal (investigational) product, whether or not related to the medicinal (investigational) product.

A treatment-emergent adverse event (TEAE) is an AE that either commenced following initiation of study treatment or was present prior to study treatment but increased in frequency or severity following initiation of study treatment.

Other untoward events occurring in the framework of a clinical study will be recorded as AEs, e.g., those occurring during treatment-free periods (including Screening or post-treatment follow-up periods; see the Schedule of Activities, [Table 3](#)) in association with study-related procedures and assessments, or under placebo. For study drugs, lack of efficacy may be an expected potential outcome and should not be reported as an AE unless the event is unusual in some way, e.g., greater in severity.

Concomitant illnesses, which existed prior to entry into the clinical study, will not be considered AEs unless they worsen during the treatment period. Pre-existing conditions will be recorded as part of the subject's medical history.

### **14.2 Adverse Event Recording**

#### **14.2.1 Coding the Adverse Event**

Standard medical terminology should be used in describing AEs. MedDRA Version 24.0 will be used as the standard coding dictionary for AEs and in describing the subject's medical history, and the World Health Organization (WHO) Drug Dictionary (B3 Global VMAR 2021) will be used to code concomitant medications. Informal descriptions should be avoided.

#### **14.2.2 Severity of Adverse Event**

The severity of an AE refers to the extent of clinical abnormalities and to the extent of which an AE affects the subject's daily activities ([Table 8](#), FDA Guidance for Industry; Toxicity Grading Scale for Healthy Adult and Adolescent Volunteers Enrolled in Preventive Vaccine Clinical Trials, 2007). The term "severity" is used to describe the intensity of an event. This is not the same as "serious". Seriousness, not severity, serves as the guide for defining regulatory reporting

obligations. The highest severity grade attained should be reported, for AEs with divergent severities.

Severity will be categorized according to event category (local, systemic, other).

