#### **12.1.10. Skin test results assessment**

Investigational products are administered in two stages at Visit 1, as described in [Section 10.4](#). In Stage 1 administration, subjects will receive the diluent (negative control), followed by the “1:10 dilution” strength of TNX-2110, TNX-2120, TNX-2130 in their left forearm, and CANDIN®

(positive control) in their right forearm. In Stage 2 administrations, subjects will receive the “undiluted” dose strength of TNX-2110, TNX-2120, TNX 2130 in the right forearm. The order and specific locations of injections are indicated in Table 4 and the Pharmacy Manual ([Appendix 5](#)). A ballpoint pen will be used to mark the arm but also describe precise location of injections (i.e., start three inches from antecubital crease).

The area of induration will be measured at injection sites on the volar aspect of each forearm ([Figure 2](#)). To ensure standardization, calipers will be used to ensure accurate measurement of induration. A member of the study team will visually inspect injection site under good light and measure the induration (thickening of the skin), not erythema (reddening of the skin). Measurements will be made across two diameters. The mean of the longest and midpoint orthogonal diameters of the indurated area should be reported as the DTH response. For example, a reaction that is 10 mm (longest diameter) by 8 mm (orthogonal diameter) has a sum of 18 mm and a mean of 9 mm. The DTH response is therefore 9 mm. The diluent (negative control) is expected to elicit a negative skin test result (i.e., <5 mm), and the CANDIN (positive control) is expected to elicit a positive skin test result (i.e.,  $\geq 5$  mm).

A digital caliper will be used to measure the area of induration as shown in above diagram. All the information (e.g., date and time of test administration, injection site location, lot number of peptide and measurement of area of induration) will be recorded in the CRF.

Further details regarding skin test administration and measurement are provided in the Pharmacy Manual ([Appendix 5](#)).

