#### **Local Adverse Events**

The injection site should be visually inspected for local reactions and observed changes should be measured and recorded as AEs on the CRF page. Subjects should be asked about their general wellbeing (i.e., not prompted by specific questions regarding symptoms and side effects) and any reports of pain and/or itching or any unexpected symptoms should be evaluated and recorded in the CRF.

Local injection site skin reactions will be captured by subject self-reported 7-point Likert scales indicating severity of: erythema (redness), pain, tenderness, pruritis (itching), and swelling.

Photography of the injection site (volar forearms) after IP administration at Visit 1 and at Visit 3, 4, and 5, or unscheduled in person visit, will be used for safety documentation of local skin reaction, such as redness and swelling, or unexpected findings such as rash, blistering and necrosis, which require assessment by the designated Investigator.

For further information with regard to AEs, please refer to [Section 14](#).

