### **Systemic Adverse Events**

Systemic adverse events will be assessed and graded using the toxicity scales defined in the FDA guidance for industry ([FDA, 2007](#)). Systemic adverse events will be graded using a 4-point system (Grade 1 = mild, Grade 2 = moderate, Grade 3 = severe, and Grade 4 = potentially life threatening). Any AEs of systemic allergic reaction will be graded according to the World Allergy Organization Grading Scale for Systemic Allergic Reactions ([Appendix 1](#)). Any reported or observed systemic AEs will be recorded on the systemic AE section of the CRF.

Medications and equipment (crash cart and adrenaline auto-injectors [EpiPen, Jext or Emerade]) to manage possible anaphylactic reactions will be available for immediate use. All investigative site staff will be trained in identifying anaphylaxis and a medically licensed professional trained in the clinical management of anaphylaxis will be present at Visit 1 for the duration of Stages 1 and 2.

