9.1. Adverse Events

Treatment emergent AEs are defined as AEs that either commenced following initiation of study treatment or was present prior to study treatment but increased in frequency or severity following initiation of study treatment. Adverse events of special interest (AESI) include anaphylactic reaction and enhanced disease from repeated exposure to SARS-CoV-2 (in subjects who have recovered from SARS-CoV-2 infection or in subjects recently vaccinated against SARS-CoV-2).

All AEs occurring after completion of the informed consent process and before the end of study, regardless of relationship to study drug, will be included and classified by system organ class (SOC) and preferred term (PT) using the Medical Dictionary for Regulatory Activities (MedDRA) v24.0.

For treatment-emergent AEs (TEAEs), the following will be summarized and presented for the Safety population:

An overall summary of TEAEs, which includes:

- a. the number and percentage of patients experiencing a TEAE
- b. the number and percentage of patients experiencing a TEAE by strongest relationship to IP
- c. the number and percentage of patients experiencing a TEAE by highest severity grade
- d. the number and percentage of patients experiencing a systemic allergic reaction by highest grade according to the World Allergy Organization Grading Scale for Systemic Allergy Reactions
- e. the number and percentage of patients experiencing a treatment emergent SAE (TESAE)
- f. the number and percentage of patients experiencing a TEAE leading to study discontinuation
- g. the number and percentage of patients experiencing a treatment emergent AE of Special Interest

In the overall summary of TEAEs table, besides tabulating the number and percentage of patients, the total number of TEAE episodes will also be provided. If a patient has repeated episodes of a particular TEAE, all episodes will be counted in the summary table.

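### SAP 9.1 pools local injection-site and systemic events in its any-TEAE, relationship and highest-grade rows and names no SOC/PT table, so non-serious, non-allergic systemic events may not be visible in any table

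*Protocol*

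**What the plan says.** **Protocol.** Section 14.2.2 handles severity by type of event: "Severity will be categorized according to event category (local, systemic, other"). Under Local Adverse Events in Section 12.1.11, site staff inspect the injection sites, and "observed changes should be measured and recorded as AEs on the CRF page". For the other category, "Any reported or observed systemic AEs will be recorded on the systemic AE section of the CRF". Sections 14.2.4 and 14.2.5 send local AEs to a subject-reported 7-point Likert scale and other events to FDA Grades 1-4. Section 13.5.1 promises counts and percentages by System Organ Class and Preferred Term, and tabulation by severity and causality.

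**SAP.** Section 9.1 classifies AEs by SOC and PT, but its list of what will be summarised contains only one overall table. The rows that matter here are:

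- (a) "the number and percentage of patients experiencing a TEAE"
- (b) the same, split by the closest link to study product assigned to any of the subject's events
- (c) "the number and percentage of patients experiencing a TEAE by highest severity grade"
- (d) systemic allergic reactions, by World Allergy Organization grade
- (e) treatment-emergent SAEs
- (f) TEAEs leading to discontinuation
- (g) "the number and percentage of patients experiencing a treatment emergent AE of Special Interest"

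No row is divided into local, systemic and other. Likert scores (9.1) and vital signs (9.3) are listed only. SAP 2.3 and Section 10 remove all efficacy analysis and leave safety alone.

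**The concern.** Each subject receives eight intradermal injections (Protocol 10.4), and by design one should react: "the CANDIN (positive control) is expected to elicit a positive skin test result" (Protocol 12.1.10). CANDIN is given fifth, after the three diluted IPs. A reaction to it that is recorded as an AE therefore starts after the first IP injection and counts as a TEAE under SAP 7.1.6. Row (a) thus mixes reactions that a skin test is meant to provoke, including those to a non-IP control, with systemic tolerability.

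If most subjects have a local event, row (a) is already near its ceiling and barely responds to systemic events. In rows (b) and (c) a local reaction can supply a subject's strongest relationship or highest grade. Safety is a primary objective and the only analysis left, so this summary carries the study's conclusion.

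**Working it through.** The plan gives no figure to reproduce here: no AE rate, and no sample-size calculation beyond 3 × 30 = 90. All rates below are assumptions.

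**Row (a).** Let L be the proportion with a local TEAE and s the proportion with a systemic TEAE, taken as independent.

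Row (a) = L + (1 − L)s. A change in s therefore appears multiplied by (1 − L).

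Take s rising from 5% to 25%. The true change is 20 points, or 6 of 30 subjects in a cohort.

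| L | Row (a), s = 5% | Row (a), s = 25% | Change (points) | Subjects of 30 |
|---|---|---|---|---|
| 10% | 14.5% | 32.5% | 18 | 5.4 |
| 30% | 33.5% | 47.5% | 14 | 4.2 |
| 50% | 52.5% | 62.5% | 10 | 3.0 |
| 70% | 71.5% | 77.5% | 6 | 1.8 |
| 80% | 81.0% | 85.0% | 4 | 1.2 |
| 84.3% | 85.1% | 88.2% | 3.1 | 0.9 |
| 90% | 90.5% | 92.5% | 2 | 0.6 |

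The 84.3% line is 43/51, the skin-response rate in the Spike-protein study cited in Protocol 5.3. It is a DTH response rate for a different antigen, not an AE rate, and serves only as one point in the range.

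**Row (c), if local AEs are given a Grade 1-4.** Assume 20% of 90 subjects have a systemic TEAE, with highest grades 1/2/3 split 60/30/10. That is 10.8, 5.4 and 1.8 subjects. Take L = 84.3%, independent of systemic events.

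- *All local events Grade 1.* A systemic Grade 1 event sets the subject's row only when there is no local event: 1 − 0.843 = 16%. Grade 2 and 3 systemic events always set it, so those rows read 5.4 and 1.8 correctly.
- *Local grades split 70/25/5.*
  - P(local ≤ 1) = 0.157 + 0.590 = 0.747, and P(local ≤ 2) = 0.958.
  - P(systemic ≤ 1) = 0.92, and P(systemic ≤ 2) = 0.98.
  - Grade 2 row = 90 × (0.958 × 0.98 − 0.747 × 0.92) = about 22.6 subjects, against 5.4 with systemic Grade 2.
  - Grade 3 row = 90 × (1 − 0.958 × 0.98) = about 5.5 subjects, against 1.8.

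In the second case, higher-grade systemic events are mostly counted at their own grade, but they cannot be told apart from local ones.

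**Row (c), if local AEs carry only a Likert score.** They do not enter the row, and nothing is masked. The SAP severity field is Grade 1-4, the protocol's local scale runs 1-7, and neither document maps one to the other. Which case applies is undefined.

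**Where else the events could appear.** Rows (d), (e) and (g) capture allergic, serious and special-interest events, and row (f) those leading to discontinuation. A non-serious fever, headache, fatigue or myalgia that meets none of these has no table of its own in the SAP, only the AE listing.

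**The case against.** Four points on the other side have force.

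- Section 14.2.2 belongs to the protocol's AE recording section. It can be read as choosing a grading scale, not as promising a table. A reader might infer that the SAP silently dropped a planned local/systemic/other tabulation. The documents do not support that, because Protocol 13.5.1 plans no such table. What 13.5.1 does promise, and the SAP's list omits, is the SOC/PT table.
- That SOC/PT table would show fever or headache apart from injection-site terms, and SAP 9.1 does classify AEs by SOC and PT. The sponsor may intend to produce it, but the list of summaries does not say so.
- The gravest systemic events are already separated in rows (d), (e) and (g). Every AE is listed with its term, grade and relationship, so with about 90 subjects a hand count is possible.
- No local AE rate is given. An intended positive-control induration need not be untoward in the sense of Protocol 14.1, although Section 12.1.11 says that observed local changes are recorded as AEs. SAP 2.3 says the induration outcome was not as anticipated, without giving a direction.

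These points limit the size and reach of the concern. They do not supply the missing table. The SAP plans no between-cohort test, so what is at stake is descriptive clarity, not power.

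**Conclusion.** The point holds as a gap in presentation. As written, no SAP table shows the incidence of non-serious, non-allergic systemic TEAEs, and rows (a)-(c) can mask it when local reactions are common. Under independence the any-TEAE row shows (1 − L) of any systemic change: 6 to 2 of 20 points at 70% to 90% local, but 18 of 20 at 10%. The effect on row (c) depends on an undefined grading rule and may be nil.

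A reader might go further and conclude that nearly every subject will have a local AE, that local reactions swamp the systemic result, or that the study cannot show systemic tolerability. The documents do not support this: the local rate is unknown, the most serious systemic events have their own rows, and the listings hold the rest.

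**What to change.** In SAP 9.1:

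1. Present rows (a), (b) and (c) separately for local (injection-site) TEAEs and for systemic/other TEAEs, by cohort and overall. Use the systemic AE section of the CRF and the coded terms. Keep the pooled row as a total.
2. State whether local AEs scored on the Likert scale enter the Grade 1-4 highest-severity row and, if so, by what rule.
3. Name the SOC/PT table promised in Protocol 13.5.1 in the list of summaries.

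The cost is a few extra table rows plus a table the protocol already commits to. The systemic split uses data already collected. The documents do not show a separate CRF field for other events, which is why systemic and other are kept together.
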